## 1. Rationale for the study, area of current scientific concern, and why the research is needed

Hemiparesis and other impairments are a frequent and disabling consequence of stroke and can lead to asymmetric and inefficient walking patterns. Training on a split-belt treadmill, which has two separate treads driving each leg at a different speed, can correct gait asymmetries post-stroke (Reisman et al. 2005, Reisman et al. 2007). However, the effects of split-belt treadmill training only partially transfer to everyday walking over ground and extended training sessions are required to achieve long-lasting effects (Reisman et al. 2009). Our previous studies suggest that the Gait Enhancing Mobile Shoe (GEMS) that has been developed in our laboratory can be used as an alternative gait training device for people with stroke ([name], Reed, and colleagues 2011, 2011, 2012, 2013).

The GEMS (Figure 1) mimics the actions of the split-belt treadmill, but can be used during over-ground walking and in one's own home, thus enabling long-term training. This GEMS does not require any external power and is completely passive; all necessary forces are redirected from the natural forces present during walking since it utilizes the wearer's weight to generate its movements. While the movements of the GEMS are similar to the split belt treadmill, and the GEMS generates a similar aftereffect, the efficacy of this shoe in modifying the gait of an individual with stroke is not yet verified. This research aims to test the GEMS on individuals with stroke to determine if the related effects that show up on healthy subjects can benefit individuals with stroke.

In this study, we will test the efficacy of the GEMS on individuals with stroke. Efficacy will be evaluated based on the change in gait coordination and also based on subjects' self-reported comfort on the device. We predict that the GEMS will result in changes to interlimb coordination of gait. Note that this is a efficacy study, not an effectiveness or safety study of the device; this distinction is made clear in a paper by Singal et al. (2014).

[figure not shown]

Figure 1: Gait Enhancing Mobile Shoe (GEMS). (top) Picture of GEMS – note that wheels are designed such that downward force (i.e. from standing) will cause them to rotate and move the shoe backwards, relative to the ground. (bottom) The motion of the GEMS from heel contact until toe off of walking. The GEMS was measured to have a smooth horizontal backward motion of approximately 6-8" (15-20 cm).

## 2. Background information, description of existing research, and information that is already known

In the United States, nearly 800,000 people suffer a stroke each year, and approximately two-thirds of these individuals survive (Lloyd-Jones et al. 2010). Many people suffer from significant and

long-lasting motor deficits that require rehabilitation. One such motor deficit that frequently occurs is hemiparesis, or a weakness on one side: among ischemic stroke survivors over 65 years old, half had some degrees of hemiparesis persisting over six months post-stroke (Kelly-Hayes et al. 2003). Lower limb hemiparesis leads to asymmetric walking patterns, called hemiparetic gait (Brandstater et al. 1983; Wall and Turnbull 1986). Specific characteristics of hemiparetic gait include asymmetries in temporal (e.g. swing time and double-support time) (Brandstater et al. 1983; Titanova and Tarkka 1995) and spatial (e.g. step length) (Balasubramanian et al. 2007) measures of interlimb coordination. That is, the timing and placement of the feet are not equal on the two sides.

The asymmetric nature of hemiparetic gait can have a large impact on functional walking ability. For example, swing phase asymmetry is a significant predictor of hemiparetic walking performance because it strongly correlates with stages of motor recovery, walking speed, and falls (Brandstater et al. 1983; Titanova and Tarkka 1995). Another measure of temporal asymmetry – double support duration – is similarly correlated with walking speed (Olney et al. 1994). In addition, spatial (e.g. step length) asymmetry is associated with decreased propulsive force on the paretic leg (Balasubramanian et al. 2007; Bowden et al. 2006), which limits forward motion of the body and reduces gait efficiency (Brouwer et al. 2009; Kahn and Hornby 2009). The importance of gait efficiency should not be understated – the elevated energy demands of hemiparetic gait combined with physical deconditioning post-stroke can greatly limit performance of activities of daily living, contributing to poor cardiovascular fitness and metabolic syndrome. In turn, this can increase the risks of a second stroke or cardiovascular event and is associated with increased morbidity and mortality rates (Ivey et al., 2005). Therefore, improving gait symmetry should be an important goal for therapy, to not only improve functional mobility and reduce injury, but also to enhance general health and well-being post-stroke.

Practicing walking on a split-belt treadmill can correct abnormal interlimb coordination of gait in individuals with hemiparesis following stroke or other central nervous system lesions (Reisman et al. 2005, Reisman et al. 2007). Asymmetric gait can manifest as a spatial asymmetry, in which steps taken on one side are longer than those on the other. It can also manifest as a temporal asymmetry, where the timing is uneven on the paretic and non-paretic sides. Temporal asymmetries are often measured as differences in the duration of double support periods, which are the amount of time both feet are simultaneously contacting the ground and are measured separately for the paretic and non-paretic sides. The GEMS is designed to cause changes in both spatial and temporal gait symmetry. We predict that the GEMS would cause the steps on the side with the GEMS to be larger since individuals would compensate for the backward rolling motion by placing their foot farther forward in stance, thus increasing the distance between the two feet. Similarly, since the stride is longer, it may also shorten the duration of stance relative to the other side. With shortened stance duration, the amount of time spent in double-support at the end of stance would likely decrease as well. An alternative is to have a GEMS that moves the foot forward, which would have the opposite effect, shortening steps and lengthening double-support durations of the foot that it is placed on. Therefore, the same effect could be obtained by using a backward-moving GEMS on the healthy-side foot as would be obtained using a forward-moving GEMS on the paretic-side foot. In this study, we will focus on the backward moving GEMS, as shown in Figure 1.

Although the original idea of the GEMS is derived from the motion of the split-belt-treadmill, there are distinct differences between walking on the GEMS and walking on a split-belt treadmill with asymmetric belt velocities ([name] and Reed, 2013). While the body's velocity relative to ground is zero on a split-belt treadmill, the relative velocity of the GEMS is non-zero and forward. The GEMS forces the wearer's foot forward or backward whereas the treadmill moves both feet backward, but at different speeds. For both the split-belt treadmill and the GEMS, the relative velocity between both feet is similar and the backward-moving GEMS takes the place of the faster tread. Our short-term study will examine how the motion of the shoe affects the change in gait.

We hypothesize that training over ground will lead to a change in the interlimb coordination in individuals with asymmetric gait and allow individuals to develop a more persistent symmetric gait.

There are several differences between training on ground and a treadmill, such as visual flow and vestibular information signaling forward movement that likely limit the expression of learning in the over-ground context when trained on a treadmill. Visual cues appear to be particularly important for context awareness (Keamey, 2003). Visual cues, coupled with prior experience, are so powerful that predictive postural responses cause an individual to stumble when stepping onto an escalator that is not moving (Reynolds and Bronstein 2003; Bronstein et al. 2009). The body has learned an internal model that expects an acceleration when stepping onto an escalator, but when that acceleration does not occur, the person stumbles. A recent study of split-belt walking showed that transfer to over-ground walking is enhanced when subjects are blindfolded during training on the treadmill and tested over ground (Torres-Oviedo and Bastian, 2010). Since blindfolding eliminates visual cues about the environment, this also suggests that vision is a key factor in determining the context-dependence of learning. Since it is not realistic to blindfold stroke patients during gait training, we designed the GEMS so that training could occur during over-ground walking, thus visual cues during training and later walking over ground would be the same.

Data from control subjects using an earlier version of the GEMS has been published ([name] et al. 2011) and a video of this previous version can be found at <http://reedlab.eng.usf.edu/publications/handzic2011GEMS.mp4>. In this study, we found that this earlier version of the GEMS was capable of changing step length as predicted, however the previous design was too heavy and too tall to be considered practical for testing in stroke populations. The current version of the GEMS produces similar motion to the previous version, but it weighs less (~1 kg) and is shorter (~4.4 cm). We will test the efficacy of wearing the current GEMS on gait coordination during walking over ground on individuals with stroke. All walking will be performed while subjects are wearing a gait belt and are closely guarded by an experienced physical therapist to prevent falling. Subjects may wear a safety harness attached to the SOLO-STEP® System (Solo-Step, Sioux Falls, SD) if necessary. The effects of the GEMS on gait coordination will be compared to those induced on a split-belt treadmill.

The proposed project represents one of the first attempts to build a device that corrects walking symmetry while walking over ground. Not only would this allow people to experience gait corrections while performing normal movements, but the simplicity and relative low cost of these devices would also open up potential opportunities to train at home (for high-functioning individuals with supervision) and in clinics where a split-belt treadmill is not available. The studies outlined here will establish whether the GEMS is capable of changing interlimb coordination of gait, and whether individuals with stroke can use these devices for rehabilitation purposes. This work will thus build the foundation for future training studies examining the effectiveness of long-term use of the GEMS for improving symmetric walking patterns.

### **3. The research questions, objectives, and purpose**

The question that this study targets is the modification of human walking patterns for use in stroke rehabilitation. It is our ultimate objective to show that the GEMS can change a person's temporal and spatial gait asymmetry into a symmetric gait. Our points of reference are results obtained by previous studies with split-belt treadmills. We are also interested in how altering the interface between a foot and the ground influences the adaptation to new walking patterns.

### **4. The study design including information that is needed to answer the research questions**

The goal of this study is to test the efficacy of the Gait Enhancing Mobile Shoe (GEMS), which we hypothesize can be used to correct gait asymmetry in individuals with stroke. The study will be structured around subjects walking on the GEMS before and after which the subjects' gait is recorded and analyzed. The study design is within-subjects where each individual's gait will be compared before, during, and after the training period. There will be three phases of this research, tests on healthy individuals, a short-term training on individuals with stroke that lasts up to four

sessions and a long-term training on individuals with stroke that lasts four weeks with an initial visit prior to the start of training and two follow-up tests at one and three months.

The tests on healthy people will consist of either one or two training sessions on the GEMS and/or split-belt treadmill with one pre-screening test to evaluate subjects' gait patterns. Some of the sessions will be used to optimize the motion of the GEMS and the after-effects prior to testing on individuals with stroke. Some of the sessions will be directly compared to the split-belt treadmill.

The short-term training will consist of three training sessions performed in one week with a gait evaluation on the last day and a pretest with initial fitting of the shoe the week before. One or two of the training sessions may be replaced with training on the split-belt treadmill in place of training on the GEMS to allow for a direct comparison in the change in gait.

The long-term training will consist of four weeks of training with three training sessions performed each week. Gait evaluations will be performed the week before the first training, periodically during training (no more than once per week), and followup tests at one and three months after final training. An assessment of the subjects ability to adapt to a split-belt treadmill may be conducted at the start and/or end of the experiment to allow a direct comparison of their gait.

The training sessions for the testing on healthy individuals and the short- and long-term trainings on individuals with stroke will consist of up to forty minutes of training over up to eight shorter sessions of walking on the GEMS with breaks between walking sessions and as needed if the subject requests an additional break. Subjects will place the GEMS on their foot in which they have the shortest step length, as measured during the pre-training gait analysis. This is typically the healthy side foot. The GEMS will encourage them to take larger steps with that foot. The total training sessions will be no longer than one hour. For split-belt treadmill sessions, the format will be exactly the same, but they will walk on a split-belt treadmill instead of the GEMS with the faster tread moving on the same foot that would wear the GEMS in the over-ground walking sessions.

A study physician or an advanced registered nurse practitioner (ARNP) will perform medical screening for the subjects that will participate in the stroke portion of this study to determine if potential subjects had one or more cerebral strokes without other medical conditions (e.g., other neurological, orthopedic, etc.) that would affect or explain the subjects' walking or limb movement. Clinical assessments will consist of vision, proprioception, pressure sensation, cognition using Folstein Mini-Mental Status Exam (Folstein et al. 1975), and lower extremity motor function test using Fugl-Meyer Assessment (Fugl-Meyer et al., 1975). Six Minute Walk Test and Timed Up and Go Test (Andersson et al., 2006) will be performed to assess changes in subjects' aerobic capacity and risk of falls, respectively, following training. Healthy subjects will be asked to walk and a pre-test of their gait asymmetry will be evaluated.

To measure gait, a ProtoKinetics Zeno Walkway (ProtoKinetics, Havertown, PA) or a motion capture system will be used. The Zeno Walkway calculates the desired gait parameters after an individual walks across it. For motion capture, we will use infrared-emitting markers placed bilaterally on different parts of the body, such as the shoulder (acromion process), pelvis (iliac crest), hip (greater trochanter), knee (lateral joint space), ankle (lateral malleolus), and toe (5th metatarsal head), to record 3D position data. The motion capture system will record the movement of these markers at 120 Hz. In addition, pressure switches may be taped to the bottom of the shoes, beneath the heel and toe, to measure durations of swing and stance phases

Our main analysis will be to compare the amount of learning (i.e. deviations from symmetry post-adaptation) to normal baseline symmetry. This will be done using a repeated measures ANOVA to compare baseline gait symmetry at the start of the experiment to post-adaptation at the end of the experiment and on the 1 and 3 month follow-ups. We will quantify the amount of adaptation and the change in gait asymmetry by comparing the magnitude of step length and double support differences during baseline, at the beginning of training, during training, and after training. During a symmetric gait, step lengths on each side are the same; during an asymmetric gait, step lengths are different. These measures are standard accepted measures for measuring gait asymmetries.

## 5. Sample size

Preliminary studies with three healthy test subjects showed statistical data that indicated that the minimum number of subjects for this study is 18 ([name] et al. 2011). We powered the t-test between pre-training and post-training data. We calculated an effect size of 0.68 for step length difference, resulting in an estimated sample size of 18 subjects. We are planning two experiments, a short-term and a long-term, so we expect to need 36 total subjects to show the necessary statistical power for each. The preliminary test with healthy subjects was approved under the Einstein Healthcare Network IRB HN4365, and other preliminary tests with healthy subjects were conducted under USF IRB Pro00001858. Similarly, for the healthy person study, we expect to need a sample size of 18 subjects.

In addition, initial testing on individuals with stroke has been approved and conducted under the Einstein Healthcare Network IRB HN4365. The protocol described here is similar, but will be performed at USF and the training will involve multiple sessions, as opposed to the earlier studies that involved a single session.

According to the 2006 American Community Survey, the percentage of females in the adult population in Hillsborough County is slightly greater than male adults (51.3% and 48.7% respectively). We have no reason to think that women and men will differ in their abilities on any of these tasks. As such, we expect to enroll approximately the same number of men and women.

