d. Compensation

Subjects will be paid \$6 plus reimbursement for travel for each completed study visit and parking passes will be provided. If they do not complete the study, they will be paid for the visits completed. They will be paid within 30 days of the end of their participation in the study.

No compensation will be provided for the healthy participants.

e. Withdraw from the research study

We will discontinue testing if the subject reports or we observe signs of discomfort or fatigue that interfere with their participation in the experiment. In any of these circumstances, the experiment will immediately stop and the subject will be compensated for his/her time. Please note that the likelihood of participants experiencing these symptoms during the experiment is not greater than in their everyday lives (e.g. during walking). Since we are performing repeated-measures statistical tests, it is essential to obtain all measures from each subject. Therefore, if a subject is unable to complete the experiment, we will remove the data from analysis. Also, if a subject requests that his/her data be withdrawn, we will delete it all electronic files from our records and destroy any paper records.

13. Data and safety monitoring plan.

The collected data will be coded so no personally identifying information will ever be attached to the data. The lookup table will be stored separately from the data. Only [name] and [name] will have access to the data and the lookup table. No one but the PI ([name]) and study staff will have access to the data used in this study. The data will be recorded to spreadsheet and/or text files. Shortly after the experiment, the data will be analyzed for completeness and integrity. It will then be copied to a remote secure server and backed up. Once a subject's experiment has been verified, it will only be looked at as part of all experiments performed in conjunction with this set of experiments, all of which will be anonymous. The analysis of the entire data set (all subjects) will occur after each experiment.

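### Removing all data from non-completers takes the long-term experiment below its own minimum of 18 and discards the pre/post data on which the sample size was built

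*Combined protocol and SAP*

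**What the plan says.** Section 5 (Sample size) states that "the minimum number of subjects for this study is 18". The basis is a pre/post comparison: "We powered the t-test between pre-training and post-training data", and "We calculated an effect size of 0.68 for step length difference, resulting in an estimated sample size of 18 subjects". For the short-term and long-term stroke experiments together, "we expect to need 36 total subjects to show the necessary statistical power for each". The healthy-subject study also has 18. Section 5 gives no alpha, sidedness, numeric power or expected dropout.

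Section 12e (Withdraw from the research study) provides for stopping a subject's testing because of discomfort or fatigue. It reasons that, for repeated-measures tests, "it is essential to obtain all measures from each subject", and concludes that "if a subject is unable to complete the experiment, we will remove the data from analysis". A separate sentence covers subjects who ask for their data to be withdrawn.

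Section 4 describes the long-term experiment as four weeks of training, with gait evaluation beforehand and follow-up tests one and three months after the final training. The main analysis is a repeated measures ANOVA of baseline, end of experiment, 1 month and 3 months.

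**The concern.** The two sections do not fit together. Section 5 treats 18 as the least that will do and adds nothing to it, while Section 12e reduces the analysed number whenever someone fails to complete. Non-completion is foreseen: Section 12d sets payment for subjects who do not finish, and Section 12e sets out when testing is stopped.

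The rule costs most in the long-term experiment. A subject can finish training, be measured before and after it, and then miss the 3-month test. Under Section 12e that subject's data leave the analysis, including the pre/post difference that Section 5 was powered on. That difference was observed, and the follow-up gap is no reason to lose it.

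Two things are at stake. A null long-term result would be read against a planned power that the analysed number does not give. The result would also describe completers only: subjects who stop because of discomfort or fatigue may respond differently, and removing them would hide that.

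**Working it through.** **Inputs from the documents.** Effect size d = 0.68; n = 18 per experiment; pre/post t-test within subjects, taken as paired (all Section 5). Deletion of non-completers (Section 12e). Four time points in the long-term main analysis (Section 4).

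**Assumed, because not stated.** Alpha 5%, shown two-sided and one-sided; target power 80% when reproducing 18; completion rates of 95%, 90% and 80%.

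**Step 1: the plan's own figure.** The normal approximation for a paired test is n = ((z_alpha/2 + z_beta)/d)² = ((1.960 + 0.842)/0.68)² = 16.97, so 17. The exact noncentral-t calculation gives 19. The stated 18 lies between them, so a two-sided 5%, 80% design is plausible. It is not the only candidate: one-sided 5% gives 17 for 85% power and 20 for 90%. A two-sample reading gives 34 per arm and does not fit.

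**Step 2: the total.** 2 × 18 = 36, which is the stated total. Nothing is left for attrition if 36 is the number enrolled.

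**Step 3: power by number analysed.** Power is the probability that a noncentral t with n − 1 degrees of freedom and noncentrality 0.68√n exceeds the critical value. At n = 18 the noncentrality is 0.68 × √18 = 2.885, and the two-sided critical value on 17 degrees of freedom is 2.110.

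| Analysed | Two-sided 5% | One-sided 5% |
|---|---|---|
| 18 | 77.6% | 86.9% |
| 17 | 74.9% | 85.0% |
| 16 | 72.0% | 82.9% |
| 15 | 68.8% | 80.5% |
| 14 | 65.3% | 77.8% |

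With 14 analysed, the effect detectable at 80% power (two-sided 5%) is d = 0.81.

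**Step 4: how likely a loss is.** If 18 are enrolled and each completes independently with probability c, the chance that all 18 are analysable is c^18. Power is averaged over the binomial number of completers.

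| Completion (assumed) | All 18 complete | Mean power, two-sided | Mean power, one-sided |
|---|---|---|---|
| 95% | 0.95^18 = 40% | 75% | 85% |
| 90% | 0.90^18 = 15% | 72% | 83% |
| 80% | 0.80^18 = 2% | 66% | 78% |

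**Step 5: what the deletion rule itself costs.** Suppose 18 are enrolled in the long-term experiment, all have baseline and post-training evaluations, and four miss a follow-up. Section 12e leaves 18 − 4 = 14 for the pre/post contrast, with 65% power (two-sided). An analysis that keeps observed data leaves 18 for that contrast, with about 78%. The difference comes from the rule and not from recruitment.

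**The case against.** The case against is substantial, and several parts of it stand.

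- **Stated power.** A reader might infer that power falls below a stated figure. Section 5 refers only to what is needed "to show the necessary statistical power for each" and gives no number. Only the minimum of 18 can be shown to be breached.
- **Enrolled or analysed.** A reader might take 36 as a fixed enrolment. The wording is an expectation of need and could mean analysable subjects.
- **Replacement.** A reader might infer that the trial has no replacement rule. Sections 8 and 9 were not in the text available for this review, so it can only be said that none appears in the rest.
- **Missed training sessions.** A reader might infer that one missed session among the twelve removes a subject. Section 12e speaks of obtaining all measures and of being unable to complete; it does not say that.
- **Every experiment equally.** The short-term experiment is a pretest and then three sessions in one week, so its exposure is much smaller.
- **Sidedness.** With a one-sided 5% test, three losses from 18 still leave 80.5%. It is therefore not shown that adequate power requires zero dropout.
- **Precision.** The effect size is tied to three healthy subjects. If 0.68 is their paired effect, its exact 95% interval runs from about −0.66 to 1.91. A drop from 78% to 72% is small beside that. The power figures are also for a t-test, while the main analysis is a repeated measures ANOVA.

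What survives is that a deletion rule is paired with a minimum that has no visible margin. This needs no assumed alpha or dropout rate. Nor does the point that missing a follow-up discards an observed pre/post difference.

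**Conclusion.** The point holds in this limited form. If 18 is the number enrolled, one non-completer in the long-term experiment takes the analysed number below the plan's own minimum, and the deletion rule makes the result completers-only. The loss of power is moderate: from 18 to 14 analysed it is about 12 percentage points two-sided (77.6% to 65.3%) or 9 one-sided (86.9% to 77.8%). Both rest on d = 0.68 being right and on an assumed alpha. How far the number falls depends on a dropout rate that the documents do not give. The main exposure is the long-term experiment. The rule should be changed before analysis, because its premise is unnecessary: repeated measures can be analysed without complete data from every subject.

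**What to change.** 1. **Section 12e.** Replace removal for non-completion with a mixed model for repeated measures that includes every subject with a baseline and at least one later evaluation. Leave the provision for subjects who ask for their data to be withdrawn as it is. Align the main analysis in Section 4 with this model.
2. **Section 5.** Say whether 18 is the number enrolled or analysed. State alpha, sidedness and the power at the number expected to be analysed, with the dropout assumption behind it.

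Neither change needs added enrolment. The costs are wording, slightly more analysis work, and reliance on a missing-at-random assumption, which may be strained for subjects stopped because of discomfort or fatigue; the report should give numbers and reasons for non-completion. The model helps chiefly with losses after training. A subject lost before the post-training evaluation still adds little to the pre/post contrast, so the power given in Section 5 should allow for those losses.
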